**Knowledge questions: Q2-Q3**

- 2 **Select true or false for the following statement on isatuximab:**  
*“Isatuximab is associated with risk of interference with blood compatibility tests”\**
  - True
  - False

[Correct answer: True]

PI- List drop down

\*Key safety question

[DP:1]

- 3 **Approximately how long may the isatuximab interference with indirect antiglobulin tests persist after the last infusion of isatuximab?**
  - A. One month
  - B. Three months
  - C. Six months
  - D. One year

[Correct answer: C]

---

PI- List drop down

[DP:1]

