## **9.4 Data Sources**

This study will require primary data collection, as the most appropriate method of data collection for the study objectives is through questionnaires. The questionnaire will be short (approximately 15 minutes). A set of standard questions will be developed for each target group. Questions will be 1) concise and understandable; 2) close-ended (e.g. yes/no/I don't know/Not-Applicable to my setting answers or true/false/I don't know answers; 3) including some traps (e.g. some questions will present false statements). The HCPs will have the possibility to fill in the questionnaire either in English or in their native language. The questionnaire in English and its translations will be validated via pilot interviews with two HCPs in each country after a user acceptance testing phase.

Questions in questionnaire will not be revealed before the HCP opens it. Once the HCP has saved their answers, they will not be allowed to go back and change the answers. Both of these strategies are in an effort to reduce the possible Hawthorne effect.

The target populations will include HCPs involved in the management and follow-up of multiple myeloma, such as haematology/oncology specialists and HCPs associated with transfusion centres.

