### 9.6.1 Data Collection

Data for this study will be collected electronically by Evidera, the owner of LiveTracker™ platform. LiveTracker™ is a cloud-based, real-time, continuous electronic data collection platform that delivers real-world evidence data. LiveTracker™ has the capability to perform automatic checks of data quality and missing-ness. The administration of measures will be conducted according to the protocol.

---

Once HCPs click on their unique online data collection form link, they will be tracked through a unique identifier within the LiveTracker™ platform. The HCP will be asked to complete the self-reported items. The questionnaire is assumed to take approximately 15 minutes to complete. Each HCP has ultimate responsibility for the self-reporting of all data entered in the LiveTracker™, and ensuring that they are accurate, complete, consistent, legible and timely (contemporaneous).

HCPs who delay in completing the survey or who do not complete all contents of the survey in a session will be encouraged to complete their forms through e-mail and/or phone reminders. Any queries to the HCPs will be monitored until resolution within the LiveTracker™ platform through the electronic query report. The survey is considered valid if all questions are completed.

A small amount of incentive payment (country-specific fair market value payments based on physician contracts through the LiveTracker™ Panel, as allowed per the local law and regulations) will be made to HCPs as a compensation for the time spent to complete the questionnaire (about 15 minutes).

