**3 Which of the following is correct regarding isatuximab interference?**

- A. Isatuximab binds to CD20 on RBCs
- B. Isatuximab binds to CD38 and may interfere with routine blood compatibility tests with potential false positive reactions in Indirect Antiglobulin Test (Indirect Coombs Test)
- C. Isatuximab does not mask the detection of antibodies to minor antigens in the patient’s serum

[Correct answer: B]

PI- List drop down

[DP:1]

-----Page Break-----

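### No scored item in Appendix C offers 'I don't know', and the True/False key question shares a page with a cueing Q3, so 80% correct can correspond to about 60% true knowledge

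*Protocol*

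**What the plan says.** Protocol section 9.4 describes the items as "close-ended (e.g. yes/no/I don't know/Not-Applicable to my setting answers or true/false/I don't know answers". Both formats given as examples contain 'I don't know'. The same section plans safeguards: "including some traps (e.g. some questions will present false statements", and "Once the HCP has saved their answers, they will not be allowed to go back and change the answers".

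Appendix C is the detailed questionnaire to which section 9.3 refers. None of its scored items (prescribers Q2-Q10, non-prescribers Q2-Q7) offers 'I don't know' or 'Not applicable'. The key question is Q2 in both versions. It begins "Select true or false for the following statement on isatuximab", allows True or False, and is keyed True. The prescriber Q3 then asks "Approximately how long may the isatuximab interference with indirect antiglobulin tests persist after the last infusion of isatuximab", and the non-prescriber Q3 asks "Which of the following is correct regarding isatuximab interference". The page-break markers put Q1-Q4 on one page for prescribers and Q1-Q3 on one page for non-prescribers.

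Section 9.6.1 adds: "The survey is considered valid if all questions are completed". Section 9.7.2 limits the primary analysis to valid questionnaires. Section 9.7.4 sets three criteria, all required: 80% of HCPs correct on the key question, 80% of prescribers correct on at least 5 of 7 behaviour items, and 80% of non-prescribers correct on at least 2 of 3. It gives the key question more weight than any other. No correction for guessing is stated.

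**The concern.** All three criteria count correct answers. An HCP who does not know has no way to say so, and an unfinished survey does not enter the primary analysis. Some non-knowers will therefore be counted as correct, and this error runs in one direction only.

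The key item is the most exposed. It has two options, it is keyed to the answer that an agreeable respondent would choose, and the next question on the same page treats the interference as given. The rule against going back takes effect only once answers are saved, so it does not stop someone reading Q3 before committing to Q2.

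At stake is the study's main conclusion. The materials could be declared satisfactory at a level of knowledge well below the 80% that the criteria appear to require. Analysis cannot repair this, because an option that was never offered and an answer that was already cued leave nothing to adjust with.

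**Working it through.** The protocol gives no figure for guessing. Its one related number is the sample size: 1.96² × 0.5 × 0.5 / 0.05² = 384.1. This reproduces the 384 of section 9.5 if 95% two-sided confidence is assumed (the level is not stated). The planned total of about 400 is used below.

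**Key question.** Let k be the share who truly know and g the chance that a non-knower answers True.
- Observed share correct = k + (1 − k)g, so the knowledge needed for 80% observed is k = (0.80 − g)/(1 − g).
- Even guessing, g = 0.5: k = 0.30/0.50 = 60%. Check: 0.60 + 0.40 × 0.5 = 0.80.
- If the Q3 stem raises g to 0.6, 0.7 or 0.8, k falls to 50%, 33% or 0%. These values of g are an assumed range; the document gives no basis for choosing among them.
- Exact binomial chance of at least 320 of 400 correct with g = 0.5: 0.011, 0.13, 0.53 and 0.91 for true knowledge of 50%, 55%, 60% and 65%.
- If every non-knower could and did choose 'I don't know', scored as not correct, the chance at 60% true knowledge would be about 1e-17 instead of 0.53.

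**Behaviour items.** Options per item, from Appendix C:
- Prescribers Q4-Q10: 3, 2, 2, 2, 2, 3, 4, so the guess probabilities are 1/3, 1/2, 1/2, 1/2, 1/2, 1/3, 1/4.
- Non-prescribers Q5-Q7: 2, 4, 2, so the guess probabilities are 1/2, 1/4, 1/2.

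Pure guessing, items independent:
- Prescribers reaching 5 of 7, by exact enumeration: 10.8%.
- Non-prescribers reaching 2 of 3: 1/16 (all three) + 3/16 (Q5 and Q7 only) + 1/16 + 1/16 = 6/16 = 37.5%.

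Partial knowledge: let each item be known with the same probability k and otherwise guessed, so P(correct) = k + (1 − k)g for that item. Solve for the k at which 80% of respondents pass.

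| Rule | With guessing | No guessing (g = 0) |
|---|---|---|
| Prescribers, 5 of 7 | 61% | 77% |
| Non-prescribers, 2 of 3 | 50% | 71% |

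Check for non-prescribers at k = 0.504: the item probabilities are 0.752, 0.628 and 0.752. Then P(at least 2) = 0.752² + 2 × 0.752 × 0.628 × 0.248 = 0.566 + 0.234 = 0.80.

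**The false-statement safeguard.** Among the prescriber True/False items (Q2, Q5-Q8), only Q6 is a false statement. A prescriber who always answers True gets the key item right and scores 3 behaviour items (Q5, Q7, Q8). To pass, two more are needed from Q4, Q9 and Q10. With random choice there, the chance is 1/12 + 1/9 + 1/36 = 22%, double the rate for pure guessing. Non-prescriber Q5 is a false statement, so the same habit gives 25% there, below the 37.5% for pure guessing.

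**The case against.** A reader might infer that the 80% threshold can be met by guessing and cueing without knowledge. The documents do not support that. Guessing alone gives 50% on the key item, 10.8% on the prescriber rule and 37.5% on the non-prescriber rule, and all three criteria must be met together. The key criterion would be met without knowledge only if the cue led at least 80% of non-knowers to answer True, which nothing in the protocol shows.

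Nor does the questionnaire display the key answer: Q3 presupposes the interference without stating the Q2 item or its key. The shared page is read from programming markers, not from a final screen. The invitation email cannot be counted as a further cue, because section 9.2.3 says only that it explains the study objective and its text is not in the document.

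Section 9.4 gives its formats as examples, and section 9.1 requires only closed single or multiple selection, which Appendix C meets. The conflict is with an illustration and not with a commitment. Even so, both illustrated formats include the option and the instrument uses neither.

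Forced guessing is not certain. The Abstract's main analysis leaves missing answers out of denominators, which contemplates skipped items, and a non-knower may abandon the survey. But under section 9.6.1 an incomplete survey is not valid, so such a person leaves the primary analysis, which also tends to raise the percentage correct.

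The planned safeguards deserve weight: false statements, locking after saving, and pilot interviews with two HCPs per country. As set out, they do not protect the key item. Each question is reported separately, so a reader can see which items are True/False but cannot tell by how much they are inflated.

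Finally, part of the distance below 80% on the behaviour rules comes from the 5-of-7 and 2-of-3 cut-offs. Even with no guessing, 77% and 71% per-item knowledge suffice.

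**Conclusion.** The point holds as an upward bias in all three success measures, most directly in the key question. With even guessing, 80% observed on that item corresponds to about 60% true knowledge. Any cue from Q3 lowers that figure by an amount that the documents do not allow one to estimate. For behaviour, the per-item knowledge at which 80% pass falls by 16 percentage points for prescribers (77% to 61%) and by 21 for non-prescribers (71% to 50%).

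These figures assume that non-knowers choose evenly among the options. The behaviour figures also assume independent items and the same knowledge level on every item. The no-guessing figures are a best case in which every non-knower would choose 'I don't know'; the real gain from adding the option would be smaller if some still guess.

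**What to change.** Reconcile Appendix C with section 9.4, in both versions of the questionnaire:

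- Add 'I don't know' to every scored knowledge and behaviour item. State that it is scored as not correct and stays in the denominator. It must not be treated as missing, because the Abstract's main-analysis rule would then drop it and restore the bias.
- Put Q2 on its own page, saved and locked before Q3 appears.
- If 'Not applicable to my setting' is also added to behaviour items, as section 9.4 illustrates, state how it counts in the 5-of-7 and 2-of-3 rules. Otherwise those rules are undefined for anyone who selects it.

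The cost is a questionnaire edit and an extra page, best made before translation and the pilot interviews. Observed percentages correct will be somewhat lower, so the 80% criteria will be harder to meet.

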**Behavior questions: Q4-Q10**

**4 Which of the following is correct regarding blood typing and screening?**

- A. Patients should not be blood typed and screened prior to start treatment with isatuximab
- B. Only select patients should be blood typed and screened prior to start treatment with isatuximab
- C. All patients should be blood typed and screened prior to start treatment with isatuximab

[Correct answer: C]

PI- List drop down

[DP:1]

-----Page Break-----

**5 Select true or false for the following statement: “*You should consider phenotyping prior to starting isatuximab treatment, as per local practice*”**

- True
- False

[Correct answer: True]

PI- List drop down

[DP:1]

**6 Select true or false for the following statement: “*If treatment with isatuximab has already started, there is no need to inform the blood bank that the patient is receiving isatuximab*”**

- True
- False

[Correct answer: False]

PI- List drop down

[DP:1]

**7 Select true or false for the following statement regarding the recommended measures of isatuximab treatment: “*In the event of a planned transfusion, notify blood transfusion centre about the risk of interference with indirect antiglobulin tests.*”**

- True
- False

[Correct answer: True]

PI- List drop down

[DP:1]

-----Page Break-----

**8 Select true or false for the following statement regarding the recommended measures of isatuximab treatment: “For timely transfusions, verify standing orders for transfusions to determine if your patient received isatuximab within the last year”**

- True
- False

[Correct answer: True]

PI- List drop down

[DP:1]

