- 1 Medical specialists, such as haematologists and oncologists who prescribe isatuximab to patients (prescribers)
- 2 HCPs who work in the blood banks and transfusion centres and provide blood product to patients treated with isatuximab (non-prescribers).

More specifically, messages that are targeting prescribers include the length of interference and the actions to take before, during and after isatuximab treatment (e.g., blood typing, blood compatibility profile in the Patient Card, manage blood transfusions); messages targeting non-prescribers include the mechanism of interference, specific types of blood compatibility test affected, and interference mitigation methods for blood transfusion.

Some countries (Australia) have established a policy for phenotype screening prior to the initiation of therapy with CD38 class agents, following the marketing approval of the first in class anti-CD38 (daratumumab) and/or methods to mitigate the risks of interference,(5) and such methods are included in the educational materials developed for isatuximab. The extent of the compliance to this risk mitigation in clinical practice, however, is not known.

It is critical to ensure that key safety precautions conveyed in the educational materials are well understood and adhered to by the HCPs (both prescribers and non-prescribers) in the real-world setting. Educational materials include a brochure ([Appendix A](#)) that will be distributed to both types of HCPs, as well as a Patient card ([Appendix B](#)) that will be provided to patients via their HCPs.

According to the GVP Module XVI – Risk minimisation measures: selection of tools and effectiveness indicators (Rev 2) dated 28 March 2017,(7) evaluating the effectiveness of aRMMs is necessary to establish whether an intervention has been effective, and, if not, why and which corrective actions are necessary.

This study is therefore designed to evaluate the following aspects of the aRMM: the process itself (i.e. to which extent the materials have been implemented as planned) and its impact on knowledge and behavioural changes in the target audience.

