### Objective

- 1) Describe the implementation of the aRMMs to the target population, the time period(s) of implementation in each participating country (starting from local regulatory approval) and materials used.
- 2) Assess the knowledge of the target audience about the risk and its management
  - Messages specific to the prescribers (HCPs in oncology/haematology)
  - Messages specific to the non-prescribers (HCPs in blood banks/transfusion centres)
- 3) Assess the behaviour of HCPs with respect to the safety messages

- Messages specific to the prescribers (HCPs in oncology/haematology)
- Messages specific to the non-prescribers (HCPs in blood banks/transfusion centres)

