## **Hypothesis**

We hypothesize that:

- At least 80% of the HCPs (both prescribers and non-prescribers) will provide correct responses to the first knowledge question, which is identified as the key question.

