**AND**

- 80% of the prescribers will provide correct responses to at least five out of seven behaviour questions.

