**AND**

- 80% of the non-prescribers will provide correct responses to at least two out of three behaviour questions.

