### REMINDER FOR BLOOD BANKS

- Identify the blood sample of your patient as containing isatuximab.

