**Behavior questions: Q5-Q7**

- 5 Select true or false for the following statement: *“In case the patient has urgent need for transfusion, Non-cross matched ABO/RhD compatible RBC units cannot be administered.”*
- True
  - False

[Correct answer: False]

PI- List drop down

[DP:1]

- 6 The interference mitigation methods such as treating reagent RBCs with dithiothreitol (DTT) is mainly to:
- A. Disrupt isatuximab binding to CD38
  - B. Destroy isatuximab so that it does not bind to CD38
  - C. Oxidize CD38 receptor bonds to prevent antibody from binding
  - D. None of the above

[Correct answer: A]

PI- List drop down

[DP:1]

- 7 Select true or false for the following statement: *“Kell-negative units should be supplied after ruling out or identifying alloantibodies using DTT-treated RBCs, this is because Kell Blood group system is also sensitive to DTT treatment.”*
- True

- False

[Correct answer: True]

PI- List drop down

[DP:1]

-----Page Break-----  
-----

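### All ten behaviour questions in Appendix C test recognition of recommended actions, so criteria 2 and 3 measure knowledge and cannot support objective 3

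*Protocol*

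**What the plan says.** Section 8 lists knowledge (objective 2) and behaviour (objective 3) as separate objectives. Objective 3 reads "Assess the behaviour of HCPs with respect to the safety messages". Section 7 says the study evaluates the educational materials for "its impact on knowledge and behavioural changes in the target audience". Section 9.5 defines the proportions of interest as those of HCPs who are knowledgeable about, and adherent to, the risk minimisation measures.

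The Hypothesis in section 8 and the threshold in section 9.7.4 join three conditions:

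1. At least 80% of HCPs "will provide correct responses to the first knowledge question, which is identified as the key question".
2. "80% of the prescribers will provide correct responses to at least five out of seven behaviour questions".
3. "80% of the non-prescribers will provide correct responses to at least two out of three behaviour questions".

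Appendix C fixes the items and the answer key. The behaviour items are Q4-Q10 for prescribers and Q5-Q7 for non-prescribers. Prescriber Q4 asks "Which of the following is correct regarding blood typing and screening". Non-prescriber Q6 begins "The interference mitigation methods such as treating reagent RBCs with dithiothreitol (DTT) is mainly to" and offers four mechanisms.

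**The concern.** Recognising that an action is recommended is a different quantity from having carried it out. The protocol itself separates the two by giving them different objectives and different success criteria. If the behaviour items have the same form as the knowledge items, criteria 2 and 3 are a further knowledge test under another name.

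At stake is what the study may conclude. Section 9.7.4 uses the three conditions together to judge the overall effectiveness of the measures. Under section 12.2 the results go to the EMA, the periodic safety report and the risk management plan. A satisfactory result on criteria 2 and 3 could be read there as evidence that HCPs take the precautions, when the survey collected nothing on that. No later analysis could recover it, because the items are fixed in the protocol and the practice data would never have been collected.

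**Working it through.** **The plan's own figure.** Section 9.5 gives 384 for 5% precision at p = 50%. With 95% confidence assumed (the level is not stated), n = z² × p(1 − p) / d² = 1.96² × 0.25 / 0.05² ≈ 384. The figure reproduces, but it has no bearing on this point, which is about what the items measure.

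**The items, read one by one (Appendix C).**

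| Item | Form | What the respondent must recognise |
|---|---|---|
| Prescriber Q4 | 1 of 3 | Which patients the typing-and-screening recommendation covers |
| Prescriber Q5 | True/false | That phenotyping is to be considered |
| Prescriber Q6 | True/false, false statement | That the blood bank does need to be told |
| Prescriber Q7 | True/false | That notifying the centre is a recommended measure |
| Prescriber Q8 | True/false | That checking standing orders is a recommended measure |
| Prescriber Q9 | 1 of 3 | The right statement about the Patient Card |
| Prescriber Q10 | 1 of 4 | What patients should be advised |
| Non-prescriber Q5 | True/false, false statement | That uncrossmatched units are not ruled out in urgent need |
| Non-prescriber Q6 | 1 of 4 | How DTT treatment works |
| Non-prescriber Q7 | True/false | The Kell-negative message and its reason |

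The count is 7 + 3 = 10 behaviour items, all keyed. None asks whether, how often or for which patients the respondent took the action.

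**Comparison with the knowledge items.** Prescriber Q2-Q3 and non-prescriber Q2-Q4 are also true/false or single-choice with a key. Nothing in the form separates the two groups. The questions about the respondent's own activity or experience are the profile and screening questions (such as Px and Px2) and receipt of the materials (Q1). None of these is a behaviour outcome.

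**What a pass shows.** A prescriber who never arranges typing and screening before the first infusion, and never hands out a Patient Card, can still score 7/7. As an illustration only, take uniform random guessing over the listed options:

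- Non-prescribers (chances 1/2, 1/4, 1/2, at least 2 correct): all three correct 0.0625; Q5 and Q7 only 0.5 × 0.75 × 0.5 = 0.1875; Q5 and Q6 only 0.0625; Q6 and Q7 only 0.0625. The total is 0.375.
- Prescribers (four items at 1/2, two at 1/3, one at 1/4, at least 5 correct): the three multiple-choice items give 1, 2 or 3 correct with probability 16/36, 7/36 and 1/36. The four true/false items give at least 4, 3 or 2 correct with probability 1/16, 5/16 and 11/16. The total is 0.0278 + 0.0608 + 0.0191 = 0.108.

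A pass therefore reflects choosing the keyed option, by recognition or by chance. It does not reflect reported practice.

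**Is it disclosed?** Section 9.9 says that data are self-reported and cannot be verified, and it discusses the Hawthorne effect. It does not say that practice is not asked about. It goes on to say that the results will reflect behaviour as well as knowledge and understanding.

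**The case against.** The strongest reply is that the protocol is consistent with itself. Criteria 2 and 3 are defined as correct responses to a number of questions, and Appendix C supplies those questions with a key. Section 9.3.4 lists behaviour as the recommended actions themselves, and the questionnaire follows that list closely. This stands: both criteria are measurable as written, and a reader who infers that they are not measured at all goes too far. What fails is the step from those scores to a statement about behaviour.

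Other inferences are tempting but not supported:

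- **That section 9.4 shows practice questions were intended.** It mentions a yes/no format with a not-applicable choice, but only as an example. It offers true/false as an equal alternative and assigns neither format to the behaviour items.
- **That the questionnaire drops a required behaviour.** Appendix A reminds blood banks: "Identify the blood sample of your patient as containing isatuximab". That action is not among the three non-prescriber behaviour messages in section 9.3.4, so Appendix C omits nothing from its own list.
- **That the gap between knowledge and practice can be sized.** The protocol gives no figure for it, so no percentage for actual practice follows.
- **That every item should become a did-you-do-it question.** Several messages are permissive or leave the choice to local practice (phenotyping, uncrossmatched units, DTT or another validated method), so a no could be fully compliant. One prescription or one supply is enough for eligibility, and section 7 puts the share of pivotal-trial patients needing red cell transfusion at 30%. Not-applicable answers to transfusion items could therefore be frequent, and the 5/7 and 2/3 rules have no provision for them. Table 3 targets only 40-100 non-prescribers.

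It is also fair to say that direct practice questions invite socially desirable answers, which sections 9.4 and 9.9 try to limit.

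**Conclusion.** The point holds as one of construct validity. All 10 of 10 behaviour items, and with them 2 of the 3 success criteria, measure knowledge of recommended actions; non-prescriber Q6 measures knowledge of a laboratory mechanism. The criteria can be computed, but they cannot support objective 3, the behavioural-change aim in section 7 or the adherent proportion in section 9.5. Criterion 1 is unaffected.

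The conclusion rests only on the wording of Appendix C and assumes nothing about how HCPs act. The guessing probabilities are illustrative and the verdict does not depend on them. The protocol does not show that behaviour is poor, only that the survey would be silent on it.

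**What to change.** **Required.** Rename the ten items and criteria 2 and 3 as knowledge of recommended actions in sections 8, 9.3.4, 9.5 and 9.7.4, and carry the change into the abstract, the purpose statement in section 7 and the labels in Appendix C. State in section 9.9 that practice is not measured, and draw no behaviour conclusion from these items. Unless practice items are added as below, objective 3 has to be reworded to match. This is an edit to the text only: data collection, sample size and calculations do not change.

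**If objective 3 is to be kept as behaviour.** Before piloting and translation, add a few self-reported practice items limited to the actions that the materials state without a local-practice qualifier, such as typing and screening before the first infusion, giving the Patient Card and informing the blood bank. Offer a not-applicable answer and exclude it from the denominator. Report these items descriptively and apart from the 5/7 and 2/3 rules, which then need no redefinition. The cost is a slightly longer questionnaire than the planned 15 minutes and some desirability bias, which section 9.9 should acknowledge. Section 9.4 still describes piloting and validation of the translations as future steps, so the change is cheap at this stage.
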